### **TARGET POPULATION**

Adult patients with histologically confirmed locally advanced and/or metastatic solid tumours and with r/r T-ALL or T-LBL for whom no standard-of-care therapy exists.

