## 4.2 STUDY ENDPOINTS

### 4.2.1 Primary Endpoints

The primary endpoint for Phase I, Part A (dose-escalation) of this study is as follows:

- The number of patients experiencing dose-limiting toxicity (DLT) during the first 28-day cycle of CB-103 treatment

The primary endpoint for Phase I, Part A (confirmatory) of this study is as follows:

- The incidence rate, severity and relationship to CB-103 of adverse drug reactions and serious drug reactions according to common terminology criteria for adverse events (CTCAE) V4.03, safety laboratory, vital signs, ECG and ECHO/MUGA assessments.

The primary endpoint for Phase IIA, Part B of this study is as follows:

- To assess tumour response rates in each expansion arm as best overall response rate (in solid tumours complete response [CR] + partial response [PR]) assessed by Response Evaluation Criteria in Solid Tumours (RECIST 1.1); in T-ALL/T-LBL patients, confirmed CR and Complete Remission with Incomplete Hematologic Recovery (CRi) assessed by the criteria according to NCCN Guidelines on Adult Acute Lymphoblastic Leukaemia (Version 1.2020).

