#### **Part A – Dose escalation (Phase I)**

Part A will be a dose-finding study based on a 2-parameter BLRM to investigate the safety and tolerability of sequentially enrolled dose cohorts of at least 3, up to 6 patients per dose cohort. Depending on the BLRM, additional patients may be enrolled in some dose cohorts. The first two patients of each dose level will be enrolled in a staggered approach with at least 1 day apart between first dosing of these patients. Subsequent patients may be enrolled concurrently, with at least 1 day apart from the second patient, whereby a dose cohort must be completed with regards to the DLT assessment period and be reviewed by the Cohort Review Committee (CRC) established for this study before further patients are dosed in the next dose cohort. The BLRM will be assessed for those patients satisfying the requirements for inclusion in the dose-determining set (DDS). After completion of a given dose cohort, or at any time the BLRM is updated, the decision to dose escalate and the actual dose and schedule chosen will depend on the recommendation of the BLRM about the highest admissible dose according to the EWOC principle and medical review of available clinical, pharmacokinetic and laboratory data. The outcome of these analyses and the respective datasets will be reviewed by the CRC consisting of the Investigators, Sponsor and CRO representatives, and independent functional experts as required (see Section 5.1.4.1). The CRC will make the decision to determine the next dose level and schedule for the next dose cohort.

Any dose level cohort that has been declared safe after the DLT period, may be expanded by individual patients in order to collect additional pharmacodynamic (PD) and pharmacokinetic (PK) information to support and/or confirm the mechanism of action and

explore doses at the currently tolerated dose level or below. These patients will be counted for the respective cohort at the future CRC meetings and will contribute towards the overall safety, PK, PD and clinical efficacy evaluation.

When the MTD/RP2D is defined, based on the decision of the CRC, approximately 45 additional NOTCH-positive patients with recurrent/metastatic ACC, breast cancer, r/r T-ALL/T-LBL, or any other solid tumour with proven Notch pathway activation will receive the MTD/RP2D dose to ascertain that optimal safety related to efficacy and pharmacodynamics in the tumour and in peripheral blood are achieved.

[figure not shown]

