## **6. STUDY POPULATION**

This study will include adult male and female patients  $\geq 18$  years. Patients must meet all of the inclusion criteria and none of the exclusion criteria in order to qualify for the study.

Adult patients with locally advanced solid tumour or haematological malignancies (surgically unresectable locally advanced or metastatic solid tumours or haematological malignancies) whose disease has progressed on at least one line of systemic therapy and for whom no standard curative therapy exists will be enrolled into Part A (Phase I dose-escalation). All participants must have histological or cytological evidence for the diagnosis of the respective cancer indication. CB-103 has been shown to cross the blood-brain-barrier in animals. All patients must be in an advanced or metastatic stage of disease after available curative therapies have failed to confer acceptable clinical benefit/risk to their advanced or metastatic cancer. Patients may be enrolled into the study and treated with CB-103 at an earlier line of treatment if they have a tumour with confirmed NOTCH pathway activation assessed by at least one diagnostic method, justifying the treatment with a NOTCH pathway inhibitor in an earlier line of treatment. This will be at the discretion of the Investigator.

When the MTD/RP2D is defined, based on decision of the CRC, the MTD/RP2D confirmatory cohort will open to include approximately 45 additional NOTCH-positive patients with recurrent/metastatic adenoid cystic carcinomas (ACC), breast cancer, r/r T-ALL/T-LBL, or any other solid tumour with proven Notch pathway activation, who will receive the MTD/RP2D dose to ascertain that optimal safety related to efficacy and pharmacodynamics in the tumour and in peripheral blood are achieved.

For the expansion arms in Part B of the study, the following are the preliminary indications for patients with NOTCH activated pathways planned:

1. Adenoid cystic carcinoma (ACC)
2. Triple negative breast cancer (TNBC)
3. Breast cancer (ER+/-, HER2+/-)
4. Osteosarcomas, Malignant glomus tumour
5. GI cancers (resistant to oxaliplatin or irinotecan-based therapy colorectal cancer, hepatocellular carcinoma)
6. r/r T-ALL/T-LBL
7. Any other cancer (haematologic or solid) with confirmed Notch pathway activation (basket arm)

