#### 1. Disease

- a. Histologically or cytologically confirmed solid tumours that are surgically unresectable, locally advanced, or metastatic, which have progressed on at least one line of systemic therapy (with the exception of ACC patients who are allowed to be systemic treatment-naïve) and for which no established therapeutic alternatives exist.

or

- b. Relapsed or refractory (r/r) T-ALL or T-LBL. Refractory patients are defined as T-ALL/T-LBL patients with  $\geq 5\%$  bone marrow blasts and/or concomitant extramedullary involvement, who have not achieved a CR after standard induction/consolidation therapy attempt. Relapsed patients are defined as T-ALL/T-LBL patients who have recurrent disease, i.e.  $\geq 5\%$  bone marrow blasts and/or concomitant extramedullary relapse, after having achieved a prior CR.
- c. For **Part A (dose-escalation)** solid tumour indications based on known frequent involvement of the NOTCH pathway activation in these indications, and tumours with an *a priori* known NOTCH1-4 pathway activation are also eligible, as defined below:
  - Breast cancer (TNBC, ER+/-, HER2+/-), GI cancers (resistant to oxaliplatin or irinotecan-based therapy colorectal cancer, hepatocellular carcinoma), osteosarcoma, ACC and malignant glomus tumour.
  - Any other solid cancer (including lymphoma) with a confirmed NOTCH1-4 activating mutation or genetic lesion.
- d. For **Part A (MTD/RP2D confirmatory cohort) and Part B expansion cohorts**, solid and haematological tumour indications with confirmed Notch pathway activation as follows:
  - ACC
  - Metastatic breast cancer (regardless of receptor status of ER/PR, HER2)
  - r/r T-ALL/T-LBL
  - Any other cancer (haematologic or solid) with a confirmed NOTCH pathway activation, after approval by the Sponsor

---

CONFIDENTIAL

May not be used, divulged, published, or otherwise disclosed without the consent of Cellestia Biotech AG

Notes:

- Patients are eligible if Notch pathway activation was determined in the past. If the Notch status is unknown, it will be determined on fresh bodily material.
  - The pathogenic character of the detected mutation/genetic alteration needs to be confirmed before the patient can be enrolled. Patients whose tumour mutations/alterations are not unambiguously pathogenic will be included at the Sponsor's discretion. Details on molecular alterations as signs of Notch pathway activation and the specific test method can be found in the laboratory manual.

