### **10.9.2 Part B - Dose Expansion, Stratified by Indication**

Part B of the study will consist of one or several expansion arm(s) with selected tumour indications. For the analysis of the expansion arms a Bayesian Hierarchical binomial-design will be applied with enrolment of at least 10 patients into each arm. With 10-20 patients enrolled into each expansion arm it is estimated that about 100-140 patients (pending of the number of arms) will need to be recruited. Patients from the MTD/RP2D confirmatory cohort of Part A that qualify for any of the expansion arms will be included into the analyses of Part B and will contribute to the total sample size per arm.

20 patients per Indication arm will give sufficient evidence to determine early signs of clinical benefit. Assuming a true response rate of 30% for exchangeable and partially-exchangeable indications (based on response criteria) the lower limit of the credible band for the point estimate would be greater equal to 19%.

The following indications for patients with NOTCH activated pathway are considered and grouped into the respective expansion arms:

1. Adenoid cystic carcinoma (ACC)
2. Triple Negative Breast Cancer (TNBC)
3. Breast Cancer (ER+/-, HER2+/-)
4. Osteosarcoma, Malignant glomus tumour
5. GI cancers (resistant to oxaliplatin or irinotecan-based therapy colorectal cancer, hepatocellular carcinoma)
6. r/r T-ALL/T-LBL
7. Any other cancer (haematologic or solid) with confirmed Notch pathway activation (basket arm)

**Table 21** Sample size consideration for potential indications

	Indication				
	1.ACC	2.TNBC	3.Breast Cancer	4. Osteosarcoma, Malignant glomus tumour	5.GI
	n/N Median; (CI)	n/N Median; (CI)	n/N Median; (CI)	n/N Median; (CI)	n/N Median; (CI)
strong homogeneity	6/20 30% (18%-43%)	6/20 30% (18%-43%)	6/20 30% (18%-47%)	6/20 30% (18% - 43%)	6/20 30% (18%- 43%)

The indications considered for the expansion arms in Part B might be adapted and/or additional arms added by a protocol amendment based on the outcome of Part A and further findings from non-clinical studies with CB-103 and the planned interim analysis, this might increase the planned sample size.

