### 5.6.2.1 Best Overall Response (BOR)

BOR is defined as the best response recorded from the first day of study treatment until disease progression/recurrence, death or end of study respectively data cut-off, whatever comes first.

Patients with solid tumours are considered responders if they have a tumour assessment status of PR or CR according to RECIST, v1.1.

The best overall response is the best response recorded from the start of the treatment until disease progression/recurrence. Best is defined as the first response when all a subject's response assessments are sorted by CR, PR, SD, PD, NE/UNK. In general, the subject's best response assignment will depend on the achievement of the measurement criteria. For subjects without a post-baseline, a non-missing response assessment will have a BOR of NE assigned. Unknown (UNK) or patients with symptomatic deterioration but without any scan will also be mapped to NE.

Patients with haematologic malignancies are considered responders if they have a haematologic malignancies status CR or CRi as per NCCN guidelines.

Any response must be confirmed not less than 4 weeks after the criteria for response are first met.

Patients without a post-baseline assessment will be considered NE. Additionally, after baseline, a change in methods will result in an assessment of not evaluable.

Patients who were enrolled in study, but did not receive any study treatment will have a best overall response 'Missing' and will be included as non-responders in the analysis of BOR.

BOR for different cancer types will be summarized by cohort for patients with Solid Tumour and for those with haematologic malignancies. The BOR information will be provided in Listing.

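### Haematologic cancers other than T-ALL/T-LBL can enter the basket arm with no response rule for the Part B primary endpoint, and Part A counts their partial responses as non-response

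*SAP*

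**What the plan says.** **Who may enter.** Criterion 1d, for the confirmatory cohort and Part B, lists ACC, metastatic breast cancer and r/r T-ALL/T-LBL, then "Any other cancer (haematologic or solid) with a confirmed NOTCH pathway activation, after approval by the Sponsor". Arm 7 of Part B repeats this: "Any other cancer (haematologic or solid) with confirmed Notch pathway activation (basket arm". Criterion 1c, for dose escalation, admits "Any other solid cancer (including lymphoma) with a confirmed NOTCH1-4 activating mutation or genetic lesion".

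Other passages are narrower. Protocol 5.1.1 says of the confirmatory cohort's remaining group that "any other solid tumour with proven Notch pathway activation will receive the MTD/RP2D dose". Section 6, the synopsis and SAP 2.1.1 agree. The synopsis target population is "Adult patients with histologically confirmed locally advanced and/or metastatic solid tumours and with r/r T-ALL or T-LBL", and criteria 1a and 1b offer only those two routes.

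**How response is scored.** For Part B, protocol 4.2.1 gives RECIST 1.1 CR plus PR for solid tumours and, for the other branch, "in T-ALL/T-LBL patients, confirmed CR and Complete Remission with Incomplete Hematologic Recovery (CRi"), under the adult ALL guideline. Section 10.6.2 has the same two branches for response rate. Appendix 7 covers RECIST and Appendix 8 covers ALL/LBL. The schedules in Appendices 1 and 2 place disease assessments under solid tumours only or T-ALL/T-LBL only.

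For Part A, protocol 4.2.2 and SAP 5.6.2.1 are worded more widely: "Patients with haematologic malignancies are considered responders if they have a haematologic malignancies status CR or CRi as per NCCN guidelines".

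**The concern.** Protocol 2.2 itself names CLL and many non-Hodgkin lymphoma subtypes as diseases with NOTCH activation, so the wide wording of 1d and arm 7 could well be used. Three things follow.

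- In Part B such a patient can be enrolled, treated and counted, but nothing says what a response is or when to look for one. Section 10.1 makes the safety set the primary population for efficacy, so the patient remains in the denominator. Section 10.8.2 also holds each interim analysis until every included patient can be categorised for response or has withdrawn.
- By default the basket arm sits among the fully exchangeable arms with the 25% bar (10.5.2). Only T-ALL/T-LBL, where response means CR or CRi, has partial exchangeability and its own 40% bar.
- In Part A a rule exists, and it counts only CR and CRi. A partial response in a lymphoma or CLL treated as a haematologic malignancy cannot make the patient a responder.

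**Working it through.** **Step 1. Set the passages side by side.**

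| Patient | Admitted by | Part A responder rule | Part B responder rule | Assessment schedule |
|---|---|---|---|---|
| Solid tumour | 1a, 1c, 1d | CR or PR, RECIST | CR or PR, RECIST | Yes |
| T-ALL/T-LBL | 1b, 1d | CR or CRi | CR or CRi | Yes |
| Other haematologic cancer | 1d and arm 7; not 1a, 1b or the target population | CR or CRi (4.2.2, SAP 5.6.2.1) | None | None |
| Lymphoma in escalation | 1c, labelled a solid cancer | RECIST or CR/CRi, depending on the label | Not applicable | Unclear |

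The third row is the gap. The fourth is an ambiguity.

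**Step 2. Reproduce the plan's own figure.** Section 10.5.2 gives logit(p_k) ~ N(mu, tau²), mu ~ N(logit 0.2, 2.5²), tau ~ half-normal(1), with binomial counts. Table 21 states a median of 30% with interval 18%-43% for arms at 6/20 (one column prints 47% as the upper limit). Numerical integration with five arms at 6/20 gives a median of 29.4%, a mean of 29.9% and an interval of 18.2%-42.7%. The model is reproduced.

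**Step 3. Illustrate the size.** The documents give no figure for the basket arm; Tables 4, 5 and 21 omit it. Assumptions, none of them from the documents: the basket arm has 20 patients, the five other exchangeable arms each stand at 6/20, T-ALL/T-LBL is left out, and six basket patients truly respond, of whom some have partial responses that are not counted.

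| Partial responses not counted | Basket count | Basket median |
|---|---|---|
| 0 | 6/20 | 29.4% |
| 1 | 5/20 | 28.0% |
| 2 | 4/20 | 26.5% |
| 3 | 3/20 | 24.8% |

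The success rule is a model point estimate above 25%. One or two uncounted responses leave the arm above it; three put it just below. With three uncounted, the other arms' medians fall by about 2 points.

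**The case against.** The strongest reply is that this is an eligibility inconsistency with perhaps no patient behind it. Criteria 1a and 1b and the target population leave no route for other blood cancers, and 1d requires sponsor approval. The synopsis also says that Part B response follows the criteria for each indication, which leaves room to choose suitable ones. In Part A, efficacy is descriptive, no hypothesis is tested (SAP 5.6.2) and all response assessments are listed (SAP 5.6.2.2), so a partial response would remain visible. Much of this stands, and it limits the size of the point. It does not close the gap: 1d and arm 7 say expressly that haematologic cancers may enter, and the synopsis refers to criteria that the protocol does not supply for them.

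A reader might infer more: that these patients will be scored by the ALL guideline in the Part B primary endpoint, and so wrongly. The documents do not support that.

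- SAP section 1 limits that SAP to Part A.
- Protocol 4.2.1 confines CR/CRi to T-ALL/T-LBL.
- The SAP sentence cites NCCN guidelines without naming the ALL one; SAP 5.6.2 ties the ALL guideline to T-ALL/T-LBL.
- Qualifying confirmatory-cohort patients are carried into Part B (10.9.2), but nothing says their Part A classification goes with them.

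Nor is it established that a partial response in an escalation-phase lymphoma never counts, since 1c calls lymphoma a solid cancer. Finally, a simple binomial chance of reaching 6/20 under some assumed patient mix would not measure the effect: the mix has no source, and the calculation ignores the borrowing in 10.5.2.

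**Conclusion.** The point holds as a gap and a contradiction. In Part B, response for haematologic cancers other than T-ALL/T-LBL is undefined; it is not shown to be wrongly scored. In Part A the written rule makes their partial responses non-responses. Eligibility for these patients is stated in conflicting ways, and lymphoma under 1c could fall under either response system.

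The size cannot be fixed from the documents. It ranges from nothing, if no such patient is approved, to enough to decide the basket arm: under the assumptions shown, three uncounted partial responses in 20 patients bring the estimate to the 25% line, and one or two do not. The spill-over to other arms is modest. The point deserves correction because the Part A rule and the eligibility text would be applied as written.

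**What to change.** First reconcile criteria 1a to 1d, the target population, the confirmatory-cohort descriptions (synopsis, 5.1.1, section 6, SAP 2.1.1) and arm 7, so that they agree on which haematologic cancers may enter. Then take one of two routes.

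- **Restrict.** Limit the last bullet of 1d and arm 7 to diseases with response criteria defined in the protocol. Keep T-ALL/T-LBL, which 1d also lists: limiting the whole of 1d to solid tumours would remove it.
- **Define.** Limit the CR/CRi rule in protocol 4.2.2 and SAP 5.6.2.1 to T-ALL/T-LBL. In protocol 4.2.1 and 8.3, the schedules and the SAPs for both parts, state which disease-specific criteria, which responder category (PR or better) and which assessment schedule apply to other haematologic cancers.

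Under either route, say which response system applies to lymphoma entered under 1c, and whether confirmatory-cohort patients are reclassified by the Part B rule when carried over. The restrictive route costs only wording. The other adds the assessments that the chosen criteria require. Either should be settled before any such patient's response is scored.

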### **8.1.2 Information to be Collected on Screening Failures**

Screen failures are defined as patients who consent to participate in the clinical trial but are not subsequently treated in the study. A minimal set of screen failure information is required to ensure transparent reporting of screen failure patients. Minimal information will be entered into the clinical database and includes demography, screen failure reasons, eligibility criteria, and any serious adverse event which occurred after ICF signature during the screening period.

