#### 3.1 Safety Set

The safety set will consist of all patients who received at least one dose of CB-103 and had at least one post-baseline safety assessment (where the statement that a patient had no adverse event on the Adverse Events eCRF constitutes a safety assessment). The safety set will be the primary population for all efficacy and safety related endpoints except determination of the dose-DLT relationship.

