#### 3.3 PK Set

The PK set consists of all patients who have at least received one dose of study drug and have at least one post-dose PK measurement.

**Note:** Patients who were screened and have signed the informed consent but did not receive any treatment will be listed including reason for screen failure and any serious adverse event that is related to study procedure. These patients will not be part of any summary table except for summarizing disposition.

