### 5.6.2 Efficacy Analysis

All efficacy endpoints will be summarized within cohort by descriptive statistics based on SS.

Tumour assessments (via CT, MRI or PET-CT, bone marrow, respectively, pending on tumour type) are scheduled for following time-points:

- At baseline
- During Cycle 2, 4, 6, etc.: on Day 15 (i.e. every 8 weeks)
- At EOT visit

Progression-free Survival (PFS) is assessed explicitly at week 24 and at EOT visit, though disease progression can be detected and recorded at any time-point.

Efficacy parameters are:

- Overall Response Rate (ORR)
- Best Overall Response (BOR)
- Time to Response (TTR)
- Duration of Response (DOR)
- Clinical Benefit Rate (CBR) at 3 months, at 6 months and at 9 months
- Progression-free Survival (PFS)
- Overall Survival (OS)

No formal hypothesis testing is planned.

All lesion and other tumour assessments will be included in the assessment of efficacy parameters.

All efficacy parameters from either the eCRF or calculated as part of statistical analysis will be listed.

In case of patients with solid tumour cancers, baseline lesion status as well as post-baseline assessments of target, non-target and new lesions will be provided. The overall response assessment as of RECIST1.1 are listed by individual cycles.

In T-ALL/T-LBL patients, baseline lesion status, tissue sites involved at baseline, post-baseline lesion status and new lesions will be listed; and so will the overall response assessments by cycle based on NCCN Guidelines on Adult Acute Lymphoblastic Leukaemia.

Patients who cannot be evaluated for response will be categorized as Not Evaluable (NE) or Unknown/Not Assessed (NA).

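### SAP 5.6.2.1 counts enrolled but never-dosed patients as non-responders in best overall response, which contradicts the Safety Set rule for efficacy and the bar on untreated patients in summary tables

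*SAP*

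**What the plan says.** The SAP covers Part A. In 5.6.2.1 it names a group, "Patients who were enrolled in study, but did not receive any study treatment", and rules that they are assigned a BOR of Missing and "will be included as non-responders in the analysis of BOR". The same section starts the BOR observation period on the first day of study treatment. It separately classes patients without a post-baseline assessment as not evaluable (NE).

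The population rules point the other way:

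- SAP 3.1 defines the set: "The safety set will consist of all patients who received at least one dose of CB-103 and had at least one post-baseline safety assessment". It then gives its role: "The safety set will be the primary population for all efficacy and safety related endpoints except determination of the dose-DLT relationship".
- SAP 5.6.2 opens with: "All efficacy endpoints will be summarized within cohort by descriptive statistics based on SS".
- SAP 5.1 also puts efficacy on the Safety Set. It makes the size of the analysis population the default denominator for percentages, unless the table shells say otherwise.
- The note in SAP 3.3 deals with patients who were screened and consented but got no treatment: "These patients will not be part of any summary table except for summarizing disposition". Protocol 10.1 has the same note.

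SAP 5.6.2.2, on ORR, does not mention undosed patients. SAP section 6 declares no change from the analysis planned in the protocol.

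**The concern.** A patient with no dose is outside the Safety Set by definition, so a programmer cannot both restrict BOR to the Safety Set and count undosed patients in it as non-responders. The SAP does not say which instruction prevails.

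Two things follow. First, the responder share in the BOR summary and the ORR for the same cohort can have different denominators, because the rule is stated for BOR only. Second, protocol 8.10.2 lets a patient who was enrolled in a lower dose cohort but not dosed re-enrol at a higher level as a new subject. Under the BOR sentence, that person could count as a non-responder in the lower cohort without taking any drug, and then count again in the cohort where treatment was given.

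**Working it through.** No figure in the documents depends on this rule, so there is nothing to reproduce. The check is one of consistency, followed by an illustration.

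**Step 1: can both rules apply to one patient?** Take a patient enrolled in a dose cohort and never dosed.

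| Source | Treatment of this patient |
|---|---|
| SAP 5.6.2.1 | In the BOR analysis, as a non-responder |
| SAP 3.1, 5.1, 5.6.2 | Not in the Safety Set, so in no efficacy summary |
| SAP 3.3 note, protocol 10.1 | Consented and untreated, so in disposition only |
| SAP 5.6.2.1, BOR definition | Has no first day of treatment, so no BOR observation period |

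The first row conflicts with each of the others.

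**Step 2: can the group exist?** The protocol synopsis (Procedures) and protocol 8.10.1 place enrolment after eligibility has been confirmed. Protocol 8.10.2 then speaks of patients enrolled in lower dose cohorts who were not dosed for reasons other than ineligibility. The group is foreseen, and its members can belong to a dose cohort. Their number is not given.

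**Step 3: how far could the BOR share move?** Let r be responders, n treated patients in the Safety Set and u undosed patients. The Safety Set share is r/n. Under the BOR sentence it is r/(n + u), which is the Safety Set share times n/(n + u). The cohort sizes below are those planned (up to 6 per escalation cohort, about 45 in the confirmatory cohort). The values of r and u are assumptions.

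| n | r | u = 0 | u = 1 | u = 2 | u = 5 |
|---|---|---|---|---|---|
| 6 | 2 | 2/6 = 33.3% | 2/7 = 28.6% | 2/8 = 25.0% | 2/11 = 18.2% |
| 45 | 9 | 9/45 = 20.0% | 9/46 = 19.6% | 9/47 = 19.1% | 9/50 = 18.0% |

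With u = 0 the two rules agree. One undosed patient multiplies the share by 6/7 = 0.857 in a cohort of 6, and by 45/46 = 0.978 in the confirmatory cohort.

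**The case against.** The best defence is that this is one stray sentence. The Safety Set is named for efficacy in three places in the SAP and again in the protocol, and an experienced programmer would follow it. Response is secondary in Part A, no hypothesis is tested, and neither document ties a Part A decision to a response threshold. Any error would lower the response share. The table shells, which were not available for this review, may fix the denominator. All of this stands, and it limits the importance of the point. It does not remove the conflict: the sentence is in the current SAP and is specific. Nor is it needed for caution, since treated patients without an assessment are already handled as NE. Patients who never took the drug carry no information on activity at a dose.

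A reader might infer more than the documents support:

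- **That ordinary screen failures enter the denominator.** Protocol 8.1.2 says: "Screen failures are defined as patients who consent to participate in the clinical trial but are not subsequently treated in the study". That makes an enrolled, undosed patient a screen failure. It does not make every screen failure enrolled. Because enrolment follows confirmed eligibility, the BOR sentence reaches only patients who qualified and were then not dosed.
- **That the ORR and its exact confidence interval change.** The Clopper-Pearson interval belongs to SAP 5.6.2.2, which does not carry the rule. ORR follows the Safety Set by default.
- **That undosed patients have no cohort to be counted in.** Protocol 8.10.2 shows that they can have one.
- **That BOR and ORR will appear side by side.** The SAP describes them in separate sections, and the layout is left to the shells.

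**Conclusion.** The sentence is wrong as written. It includes patients whom the declared efficacy population excludes and whom SAP 3.3 and protocol 10.1 confine to disposition. The consequence is limited: the BOR responder share and the ORR for a cohort may not share a denominator, and a re-enrolled patient could be counted twice.

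The size is unknown. One undosed patient takes 2 responders in 6 from 33.3% to 28.6%, under assumed counts. In a cohort of 45 with 9 responders, one to five undosed patients take 20.0% to between 19.6% and 18.0%. The effect is zero if every enrolled patient is dosed. No test, stated sample size or dose decision is affected. The point is minor, but it should be corrected because the result would otherwise depend on which sentence is programmed.

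**What to change.** Delete the sentence on untreated patients from SAP 5.6.2.1. In its place, state that BOR and ORR both use the Safety Set as denominator, that Safety Set patients with no post-baseline tumour assessment are kept as NE and counted as non-responders, and that enrolled but undosed patients appear in disposition only.

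The replacement text should give the Safety Set in full, including the post-baseline safety assessment. A dosed patient without one is outside the set, whereas the protocol synopsis divides the T-ALL/T-LBL response rate by patients treated. The two bases can therefore differ slightly, and the SAP should say which applies.

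The cost is one sentence removed and a short statement added, with a check that the shells agree. Data collection and sample size are unaffected. If the SAP is not reopened, the choice can be described and justified in the clinical study report, as SAP section 6 allows. Defining a separate enrolled set for BOR would also be coherent, but it would require changes to SAP 3.1, 3.3, 5.1 and 5.6.2 and to protocol 10.1, for little gain.
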